8.3.1.5.2 Reporting Serious Adverse Events

The Sponsor is required to inform regulatory authorities of SAEs that meet specific criteria. Therefore, the Sponsor must be notified immediately regarding any SAE that occurs after informed consent is obtained.

For the initial SAE report, the Investigator will complete, sign, and date a Serious Adverse Event Form and submit via fax or email within 24 hours of becoming aware of the event.

As a minimum requirement, the initial notification should provide the following information:

- Study number
- Patient number
- Gender
- Date of birth
- Name of investigator and full study site address
- Details of SAE
- Criterion for classification as "serious"
- Study drug code, or name if unblinded, and treatment start date and stop date, if applicable

- Date of SAE onset
- Causality assessment (if sufficient information is available to make this classification)

The Sponsor will request clarification of omitted or discrepant information from the initial notification. The Investigator or an authorized delegate is responsible for providing the requested information to the sponsor within 24 hours of the Sponsor's request.

Initial reports of SAEs must be followed later with detailed descriptions, including clear photocopies of other documents as necessary (eg, hospital reports, consultant reports, autopsy reports), with the study patient's personal identifiers removed. All relevant information obtained by the Investigator through review of these documents will be recorded and provided to the Sponsor within 24 hours of receipt of the information. If a new SAE Report Form is provided, then the Investigator must sign and date the form.

The SAE reporting contact information will be provided to all participating study sites by the contract research organization (CRO) on behalf of the Sponsor before study initiation.

8.3.2 Pregnancy

Pregnancy is not regarded as an AE unless there is a suspicion that an investigational product may have interfered with the effectiveness of a contraceptive medication. Any pregnancy that occurs in a patient or partner of a patient during study participation must be reported by completing a Pregnancy Reporting Form. The patient must stop study drug immediately after pregnancy is discovered and have an ET visit as soon as possible. Additionally, each pregnancy must be reported to ITI within 2 weeks of learning of its occurrence. The pregnancy must be followed up to determine outcome (including spontaneous miscarriage, elective termination, normal birth, or congenital abnormality) and status of mother and child, even if the patient was discontinued from the study.

Pregnancy complications and elective terminations for medical reasons should not be reported as an AE or SAE. If the pregnancy is associated with an SAE (eg, spontaneous miscarriage or if the mother is hospitalized for hemorrhage), a separate SAE form must be filed as described in Section 8.3.1.5.2 with the appropriate serious criterion (eg, hospitalization) indicated in addition to the Pregnancy Reporting Form.

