8.3.1 Adverse Events

8.3.1.1 Definition of Adverse Event

An AE is any untoward medical occurrence associated with the use of a drug in humans, whether or not considered drug-related. An AE can therefore be any unfavorable and unintended sign (including an abnormal laboratory finding, for example), symptom, or disease temporally associated with the use of a medicinal product, whether or not it is considered related to the medicinal product (ICH-E2A; 21 CFR 312.32[a]).

NOTE: Medical procedures scheduled prior to obtaining informed consent but occurring during the study should not be captured as AEs but the medical reason for the procedure should be listed in the medical history if related to a pre-existing condition.

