8.3.1.2 Definition of Serious Adverse Event

An SAE is defined as any untoward medical occurrence that at any dose:

- Results in death;
- Is life threatening;

Note: The term "life threatening" refers to an event in which the patient is at risk of death at the time of the event.

- Requires hospitalization or prolongation in existing hospitalization;
- Results in persistent or significant disability or incapacity; or
- Is a congenital anomaly or birth defect.

Important medical events that may not result in death, be life threatening, or require hospitalization may be considered serious when, based on appropriate medical judgment, they may jeopardize the patient and may require medical or surgical intervention to prevent one of the outcomes listed in this definition. Examples of such medical events include allergic bronchospasm requiring intensive treatment in an emergency room or at home, blood dyscrasias or convulsions that do not result in patient hospitalization, or the development of study medication dependency or drug abuse.

Emergency room visits that do not result in hospitalization should be evaluated for one of the other serious outcomes to determine whether they qualify as SAEs.

Pre-planned hospitalizations (eg, elective procedures for pre-existing conditions that did not worsen, such as cosmetic surgery and hysterectomy) are excluded from SAE reporting.

Expectedness of SAEs

The Sponsor or designee will be responsible for determining whether an SAE is expected or unexpected. An SAE will be considered unexpected if the nature, severity, or frequency of the event is not consistent with the risk information previously described for the intervention as documented in the Investigator's Brochure.

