8.3.1.5 Adverse Event Reporting Procedures

8.3.1.5.1 Reporting Adverse Events

All AEs, including overdose of study medication or other medication, must be recorded on the appropriate AE reporting page of the patient's eCRF whether or not they are considered causally related to study medication. For every AE, the Investigator must:

- Provide an assessment of the seriousness of the event (ie, is it an SAE?), as well as the severity and casual relationship. See Section 8.3.1.2 for the definition of SAEs and Section 8.3.1.5.2 for SAE reporting procedures.
- Document all actions taken with regard to study medication
- Detail any other treatment measures taken for the AE

Any AEs that are ongoing at the time of the final protocol-defined study visit will be followed until the condition returns to pre-study status, has resolved or stabilized, or can be explained as being unrelated to study medication.

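### Protocol 8.3.2 bars AE and SAE reporting of pregnancy complications and medically indicated terminations, against its own next sentence and the general AE rules

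*Protocol*

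**What the plan says.** Section 8.3.2 of the protocol opens by setting pregnancy itself apart: "Pregnancy is not regarded as an AE unless there is a suspicion that an investigational product may have interfered" with a contraceptive. Pregnancies in patients and in their partners go on a Pregnancy Reporting Form and are notified to the sponsor within 2 weeks of the site learning of them. Outcome and the status of mother and child are then followed.

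The next paragraph has two sentences. The first reads: "Pregnancy complications and elective terminations for medical reasons should not be reported as an AE or SAE". The second begins with a condition, that the pregnancy is associated with an SAE, and gives examples: "spontaneous miscarriage or if the mother is hospitalized for hemorrhage), a separate SAE form must be filed". It sends the site to section 8.3.1.5.2 for that form and adds that the pregnancy form is still needed.

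The general rules are in section 8.3.1. Section 8.3.1.1: "An AE is any untoward medical occurrence associated with the use of a drug in humans, whether or not considered drug-related". Section 8.3.1.2 lists among the serious criteria "Requires hospitalization or prolongation in existing hospitalization" and "Is a congenital anomaly or birth defect". Section 8.3.1.5.1: "All AEs, including overdose of study medication or other medication, must be recorded", whether or not thought to be caused by the drug. Section 8.3.1.5.2 asks for the SAE form within 24 hours. Section 8.3.1.4 sets the period: from consent to 30 days after the final planned visit, or after the last known dose if that visit does not take place.

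**The concern.** The two sentences give a site opposite instructions for one event. Hemorrhage in pregnancy that puts the mother in hospital is a complication of pregnancy, so the first sentence says not to report it as an SAE and the second says to file the SAE form. The first sentence also removes from AE reporting a class of events that section 8.3.1.1 covers.

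What is at stake is safety capture. A site that stops at the first sentence may not send a 24-hour report that the sponsor needs for its own duties to regulators, and the event may be missing from the SAE summary and listing planned in SAP section 10.1. Non-serious events may never reach the AE pages at all.

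**Working it through.** No arithmetic applies. The check sets the texts side by side for each kind of event, in a trial patient and within the period in section 8.3.1.4.

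| Event | 8.3.2, first sentence | 8.3.2, second sentence | 8.3.1.1, 8.3.1.2 and 8.3.1.5 | Result |
|---|---|---|---|---|
| Serious complication, such as hemorrhage with hospitalization | Not an AE or SAE | SAE form required | SAE, form within 24 hours | Direct conflict inside 8.3.2 |
| Non-serious complication | Not an AE or SAE | Does not apply | AE, to be recorded | Conflict, with no exception to resolve it |
| Medical condition behind a termination | Termination not an AE or SAE | Applies only if an SAE is associated; terminations not named | AE, or SAE if a serious criterion is met | Off the AE pages if not serious; conflicting signals if serious |

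**Step 1: is the first sentence qualified?** No. It contains no wording that limits it to non-serious events and no pointer to the sentence that follows. It names SAEs expressly. If serious complications were meant to be reported, that mention has no clear function.

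**Step 2: how far does the second sentence reach?** Its trigger is any pregnancy associated with an SAE, and its two cases are introduced as examples. It therefore covers every serious criterion in section 8.3.1.2. It does nothing for events that are not serious.

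**Step 3: does an exclusion elsewhere justify the first sentence?** Section 8.3.1.1 excludes procedures scheduled before consent. Section 8.3.1.2 excludes "Pre-planned hospitalizations (eg, elective procedures for pre-existing conditions that did not worsen" and similar cases. The opening of section 8.3.2 excludes pregnancy as such. None of these covers a complication that arises during the study.

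**Step 4: terminations.** The procedure may reasonably be left out as an AE. The condition that led to it is different. Where that condition is itself a complication of pregnancy, the first sentence bars it by name. Where it is a fetal anomaly, the congenital-anomaly criterion of section 8.3.1.2 comes into play while the first sentence says the termination is not an SAE.

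**Step 5: does the SAP settle it?** No. SAP section 10.1 defines treatment-emergent events and the AE and SAE tables, and has no pregnancy rule.

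**Step 6: how much reaches the tables?** Little. Inclusion criterion 5 requires highly effective contraception or non-childbearing potential, and participation is about 10 weeks. Study drug stops once a pregnancy is discovered, and treatment-emergent status ends one day after the last dose. Most complications would therefore fall outside the treatment-emergent tables. The SAE summary and listing are the outputs more likely to miss an event.

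**The case against.** The best defense is that the paragraph should be read whole: complications go on the pregnancy form by default, and an SAE form is added when the event is serious. The second sentence states its condition and points to the 24-hour procedure, so harm requires a site to act on one sentence and ignore the next. This has force and is a fair account of what may have been intended. It does not remove the words in the first sentence that forbid SAE reporting, and it leaves the non-serious events unaddressed.

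Other points stand in part. The protocol does not define pregnancy complications, and section 8.3.2 lists miscarriage as an outcome, so the hemorrhage example carries the contradiction more securely than the miscarriage example. A specific carve-out from a general definition is legitimate if it is deliberate, but this one is followed at once by text that undoes part of it. For a partner, who takes no study drug, the pregnancy form is the natural route and the AE definition fits less clearly. Follow-up of outcome and of mother and child means that the information need not be lost, only left off the AE and SAE pages.

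A reader might infer two stronger claims that the documents do not support. One is that the deadline for a serious complication moves from 24 hours to 2 weeks. The 2-week limit runs from learning of the pregnancy. It is not a deadline for a complication, and section 8.3.2 sets no separate one. The other is that the second sentence rescues only some serious cases. Its trigger is any associated SAE, and its examples are not a closed list.

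**Conclusion.** The point holds as a wording conflict in a reporting rule. For serious complications, section 8.3.2 gives contradictory instructions, and a site relying on the first sentence could omit the 24-hour form. For non-serious complications in a trial patient, and for the condition behind a medically indicated termination, the rule departs from sections 8.3.1.1 and 8.3.1.5.1 even on the generous reading.

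The importance is low. Few events are expected, on the grounds that contraception is required and participation is short. The documents give no pregnancy rate, so this is a judgment and not an estimate. No endpoint, efficacy analysis set or efficacy conclusion is affected. The verdict assumes that hemorrhage in pregnancy counts as a pregnancy complication in the ordinary sense, and it is confined to trial patients within the period in section 8.3.1.4.

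**What to change.** Reconcile the two sentences by replacing them with one such as: *Pregnancy itself is not an AE; any complication of pregnancy in a trial patient, or medical condition leading to a termination, that meets 8.3.1.1 or 8.3.1.2 within the reporting period in 8.3.1.4 is reported as an AE or SAE in addition to the Pregnancy Reporting Form.* Keep the existing exception for suspected interference with a contraceptive, and keep the pointer to section 8.3.1.5.2 for serious events. State separately how events in a partner's pregnancy are handled.

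The cost is one or two sentences in a protocol amendment or a clarification letter to sites. There is no new visit, test or data collection form. If any pregnancy has already been reported, the sponsor should check that associated events were not left off the AE and SAE pages.

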8.3.3 ECG Assessments

A 12-lead ECG will be performed during the Double-blind Treatment Period at the visits specified in the Schedule of Evaluations (Section 1). ECGs will be performed and electronically transmitted to a central ECG laboratory for analysis according to the instructions provided by the central ECG laboratory. Measurements (in msec) will be recorded for the following parameters: PR interval, QRS duration, and uncorrected QT

interval; QTcB (Bazett corrected QT interval) and QTcF (Fridericia corrected QT interval) will be calculated.

The overall interpretation and determination of the clinical significance of ECG findings using the interpretation from the central ECG laboratory will be the responsibility of the Investigator and will be recorded in the patient's eCRF. For eligibility criteria, the values reported on the central ECG interpretation report, not the values that are printed on the tracing itself, are used.

8.3.4 Vital Sign Assessments

Vital signs (pulse rate, systolic and diastolic blood pressure [BP], body temperature, body weight, and waist circumference) will be assessed at every visit. Height will be assessed at Screening/Visit 1 only; BMI will be calculated at Screening/Visit 1 and Visit 8/ET.

BP and radial pulse rate will be measured twice: once in the supine position for at least 5 minutes followed by once in the standing position. The standing measurements should be assessed after at least 2 minutes to allow the BP to equilibrate in the standing state.

BP may be measured manually or by machine, but radial pulse rate should only be measured manually and for a sufficient time to acquire an accurate measurement.

Patients should be instructed not to wear clothing with tight sleeves when they come for clinic visits. Additionally, patients should be kept as calm and undisturbed as possible while BP and pulse rate measurements are taken (eg, there should be no talking while the BP is being measured). The same arm and BP cuff (appropriate to the arm circumference) should be used for all BP measurements.

Whenever possible, the patient's weight should be measured at the same time of day; the patient should wear his/her usual indoor clothing but take off his/her jacket and shoes. For each patient, body weight should be determined using the same equipment during the study after ensuring its proper calibration.

8.3.5 Clinical Laboratory Evaluations

Blood and urine samples for clinical laboratory tests will be collected during the study as detailed in the Schedule of Evaluations (Table 1-1). During screening, the Investigator/sub-Investigator should assess the clinical significance of any values that are outside the reference ranges provided by the central laboratory; patients with abnormalities judged to be clinically significant will be excluded from the study. Laboratory results should be reviewed by the Investigator/sub-investigator throughout the study.

Patients are required to fast overnight (\geq 10 hours) before arriving at the study site for appointments involving the collection of clinical laboratory blood tests.

The following clinical laboratory analytes will be evaluated:

Hematology: hematocrit; hemoglobin; HbA_{1c} (Screening/Visit 1 and Visit 8/ET); red blood cell count with indices (mean corpuscular volume, mean corpuscular hemoglobin, and mean corpuscular hemoglobin concentration); reticulocytes; white blood cell count and differential (neutrophils, lymphocytes, monocytes, eosinophils, and basophils) reported as percent (%) and absolute values; and platelet count.

Clinical chemistry: albumin; alkaline phosphatase; blood urea nitrogen; gammaglutamyl transferase; calcium; creatinine; glucose; insulin; cholesterol (high-density lipoprotein [HDL] and low-density lipoprotein [LDL] [calculated] and LDL will be reported, and LDL will be reflexed if a patient's triglycerides are >400 mg/dL); triglycerides; phosphate; potassium; prolactin; ALT; AST; lactate dehydrogenase; sodium; chloride; bilirubin (total, direct); total protein; uric acid; creatine phosphokinase; and TSH (reflex free T3 and free T4 at Screening/Visit 1 and at Visit 8/ET only).

Urinalysis: macroscopic (pH, specific gravity, glucose, protein, ketones, nitrates, blood) and microscopic (red blood cells/high-power field, white blood cells/high-power field, casts, epithelial cells, crystals, granulation).

8.3.5.1 Hepatitis Screening

Blood samples will be collected at screening from all patients in order to perform hepatitis B surface antigen, hepatitis B core antibody IgM, and hepatitis C antibody (immunoglobulin G) testing. Test results will be sent to the study site and must be reviewed before Baseline (Visit 2, Day 1). Any patient who tests positive for hepatitis B surface antigen and/or hepatitis B core antibody IgM or positive hepatitis C antibody with a positive confirmatory hepatitis C RNA result will be excluded from participating in the study. Details regarding sample collection, processing, and shipping are provided in the Laboratory Manual.

8.3.5.2 Urine Drug and Alcohol Screening

Urine drug (amphetamines, barbiturates, benzodiazepines, cannabinoids [THC], cocaine metabolites, methadone, opiates, phencyclidine, propoxyphene) and alcohol tests will be performed. Any patient who tests positive for alcohol or any drug, excluding prescription benzodiazepines, prescription opiates, and cannabinoids, at screening will be excluded from participating in the study. Positive drug screen results may undergo confirmative

testing. Repeat testing is prohibited for positive alcohol, cocaine, phencyclidine, and amphetamine results.

Additional information regarding sample collection, processing, and shipping is provided in the Laboratory Manual.

8.3.5.3 Urine and Serum Pregnancy Test

Female patients who are of childbearing potential will undergo serum and urine pregnancy tests at the study clinic at Screening (Visit 1), at Baseline (Visit 2, Day 1), and, at the discretion of the Investigator, at an Unscheduled Visit. At Visit 5 and Visit 8/ET, urine pregnancy tests will be administered.

Serum pregnancy testing will be performed using blood collected as part of protocolspecified sample; urine pregnancy testing will use a urine dipstick.

If the urine and serum pregnancy tests at screening are positive, the patient will not be eligible to participate in the study. If a urine pregnancy test is negative and the associated serum pregnancy test is positive, the patient will be discontinued from the study.

8.3.6 Other Safety Assessments

8.3.6.1 Extrapyramidal Scales

8.3.6.1.1 Abnormal Involuntary Movement Scale

The AIMS (Guy 1976) measures facial and oral movements, extremity movements, and trunk movements. Seven items are rated on a scale from none (0) to severe (4). A score of "mild" in 2 or more categories or a score of "moderate" or "severe" in any 1 category results in a positive AIMS score (ie, the scores are not averaged). Additionally, overall severity is scored on the basis of severity of abnormal movements and incapacitation due to abnormal movements. The patient's awareness of and distress caused by the abnormal movements are also noted. The AIMS is to be completed at baseline and periodically in the study according to Schedule of Events (Table 1-1).

8.3.6.1.2 Barnes Akathisia Rating Scale

The BARS is a rating scale for drug-induced akathisia developed by Barnes (1989). It includes the rating of observable restless movements, the subjective awareness of restlessness, and the distress associated with the akathisia. There is also a global rating for severity. The scale is completed by the investigator or an expert site-based rater after a standard examination. Objective akathisia, subjective awareness and subjective distress are rated on a 4-point scale from 0 to 3, yielding a total score from 0 to 9. The

Global Clinical Assessment of Akathisia is rated separately, on a 5-point scale from 0 to 4. The BARS is to be completed at baseline and periodically in the study according to Schedule of Events (Table 1-1).

8.3.6.1.3 Simpson-Angus Scale

The SAS is a measure of extrapyramidal side effects (Simpson and Angus 1970). Ten items including rating gait, arm dropping, shoulder shaking, elbow rigidity, wrist rigidity, leg pendulousness, head dropping, glabella tap, tremor, and salivation are rated on a scale from 0 (normal) to 4 (extreme in severity). The SAS should be conducted by the investigator or an expert site-based rater in a room where the patient can walk a sufficient distance to allow a natural pace (eg, 15 paces). Each side of the body should be examined. The SAS is to be completed at baseline and periodically in the study according to Schedule of Events (Table 1-1).

8.3.6.2 C-SSRS

The C-SSRS is a clinician-rated instrument that reports the severity of both suicidal ideation and behavior (Posner, 2011). Suicidal ideation is classified on a 5-item scale:

- 1 (wish to be dead)
- 2 (nonspecific active suicidal thoughts)
- 3 (active suicidal ideation with any methods [not plan] without intent to act)
- 4 (active suicidal ideation with some intent to act, without specific plan); and
- 5 (active suicidal ideation with specific plan and intent).

The C-SSRS also captures information about the intensity of ideation, specifically the frequency, duration, controllability, deterrents, and reasons for the most severe types of ideation.

Suicidal behavior categories are:

- Actual attempt
- Interrupted attempt
- Aborted attempt
- Preparatory acts or behavior
- Presence of suicidal behavior

More than 1 classification can be selected provided it represents separate episodes. For actual attempts only, the actual or potential lethality is classified for the initial, most lethal, and most recent attempts.

The C-SSRS will be completed at all study visits. At Screening (Visit 1), the C-SSRS will be completed for the patient's lifetime history of suicidal ideation and behavior ("Baseline/Screening" version). At all other visits, the C-SSRS will be completed for suicidal ideation and behavior since the previous visit ("Since Last Visit" version). Before the patient leaves the study site, the Investigator or appropriately qualified designee will assess the patient's C-SSRS results.

The patient should not be released from the study center until the results of the C-SSRS are reviewed and the patient is not considered to be at risk. If there is doubt about whether a patient is at risk, the Investigator must obtain appropriate psychiatric consultation. The results of the C-SSRS will be recorded in the eCRF.

